9.4.4 SAFETY ANALYSES

AEs and SAEs will be recorded by the study team when they become aware. Adverse events leading to premature discontinuation from the study intervention and serious treatment-emergent AEs will be presented in a table.

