3. There is a risk that an IUD could be placed when a woman is already pregnant. This is true only during the standard of care and it is a potential benefit of the EPP that women cannot yet be pregnant so soon after delivery (ovulation can't occur until at least 25 days postpartum). Any woman who is > 25 days postpartum who has an IUD placed will be assessed for the risk of new pregnancy (will be asked if she has had unprotected intercourse and will be assessed for lactational amenorrhea). If > 25 days postpartum and at risk for pregnancy, then a urine pregnancy test will be done prior to IUD placement and an IUD will not be placed if a urine pregnancy test is positive until new pregnancy has been excluded. A clinician will see the patient and evaluate whether the positive

pregnancy test represents a new pregnancy or residual positive pregnancy test from the recently delivered pregnancy.

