6 STUDY INTERVENTION

6.1 STUDY INTERVENTION

Control: IUD placed 6-8 weeks postpartum (standard of care, interval placement)

Intervention: IUD placed 2-4 weeks postpartum (early postpartum placement, EPP)

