8 STUDY ASSESSMENTS AND PROCEDURES

8.1 EFFICACY ASSESSMENTS

a. Admission/Enrollment Procedure

All women in the 4 study health centers are educated about postpartum contraception during antenatal care. All postpartum women who do not receive an IPP IUD or tubal ligation will be asked if they are interested in the IUD for contraception while on the postpartum floor. If they plan to choose an IUD they will be asked for verbal assent to be pre-screened for the study. If a woman gives verbal consent to be pre-screened, a research assistant will administer the Pre-Participation Questionnaire/Eligibility Checklist. Women who meet inclusion criteria, meet no exclusionary criteria, and want to participate, will be formally consented to participate in the study. Signed informed consent forms will be collected. Subjects will be given copies of the consent document and a copy of the "Experimental Subject's Bill of Rights," and a HIPAA Authorization form for medical data to be released for research purposes. Enrolled participants will then be randomized to EPP or Interval PP IUD placement within 10 days of delivery. The Research Assistant (RA) will open the sealed envelope with the appropriate randomization envelope for the assigned participant number to unblind the participant to her assigned group. Participant numbers are assigned sequentially by each site. Participants will then be asked to complete the Baseline questionnaire.

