8.3.4 TIME PERIOD AND FREQUENCY FOR EVENT ASSESSMENT AND FOLLOW-UP

The occurrence of an adverse event (AE) or serious adverse event (SAE) may come to the attention of study personnel during study visits and interviews of a study participant presenting for medical care, by communication from the participant to the study team, or upon review by a study monitor.

All AEs including local and systemic reactions not meeting the criteria for SAEs will be captured. Information to be collected includes event description, time of onset, clinician's assessment of severity, relationship to study product (assessed only by those with the training and authority to make a diagnosis), and time of resolution/stabilization of the event. All AEs occurring while on study must be documented appropriately regardless of relationship. All AEs will be followed to adequate resolution.

Any medical condition that is present at the time that the participant is screened will be considered as baseline and not reported as an AE. However, if the study participant's condition deteriorates at any time during the study, it will be recorded as an AE. Changes in the severity of an AE will be documented to allow an assessment of the duration of the event at each level of severity to be performed. AEs characterized as intermittent require documentation of onset and duration of each episode.

At each study visit, the investigator will inquire about the occurrence of AE/SAEs since the last visit. Events will be followed for outcome information until resolution or stabilization.

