9.3 POPULATIONS FOR ANALYSES

The following datasets will be utilized for analysis:

- Intention-to-Treat Analysis Dataset: All participants randomized with known outcomes at the 6 month follow up visit*.
- Modified Intention-to-Treat Analysis Dataset: Participants who received an IUD within 6 months of delivery with known outcomes at the 6 month follow up visit*.
- Per-Protocol Analysis Dataset: Participants who received an IUD within the specified timeframe as designated by their group assignment with known outcomes at the 6 month follow up visit (14-28 days in the early group and 42-56 days in the interval group)*.

*participants known to have an IUD outcome by ultrasonography, pelvic examination, or a contact up to 240 days postpartum will be included.

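### Section 9.4.4 restricts serious events to treatment-emergent ones without defining the term; on its usual meaning, background postpartum SAEs are counted unequally between arms

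*Combined protocol and SAP*

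**What the plan says.** The safety analysis in section 9.4.4 is a single table: "Adverse events leading to premature discontinuation from the study intervention and serious treatment-emergent AEs will be presented in a table". The section gives no definition of treatment-emergent, no start date, no denominator and no time at risk, and the term is not defined elsewhere in the protocol.

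The intervention is defined by when the device is placed. Section 6.1 gives "IUD placed 2-4 weeks postpartum (early postpartum placement, EPP" for one arm and "IUD placed 6-8 weeks postpartum (standard of care, interval placement" for the other. Section 9.3 puts these windows in days: "14-28 days in the early group and 42-56 days in the interval group". Randomisation comes earlier and at the same time in both arms. Section 8.1 says: "Enrolled participants will then be randomized to EPP or Interval PP IUD placement within 10 days of delivery". Follow-up runs to 6 months postpartum (section 4.3), so it is counted from delivery and not from insertion.

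Collection is wider than tabulation. Section 8.3.4 says: "All AEs occurring while on study must be documented appropriately regardless of relationship". It treats only conditions present at screening as baseline, and it has the investigator ask at each visit about events since the last one. Section 7.1 keeps women who decide against an IUD under observation. Section 8.1 lists pregnancy among the things assessed at the 6-month visit.

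**The concern.** The randomised factor is the time of placement. If treatment-emergent means onset after insertion, the rule that decides which serious events are tabulated depends on that same factor. Consider a serious event unrelated to the device, such as an inpatient hospitalisation (serious under section 8.3.2) or a venous thromboembolism (listed in section 8.2), between days 28 and 42 after delivery. In an early-arm woman treated on schedule it is tabulated as a serious treatment-emergent event. In an interval-arm woman treated on schedule it precedes her IUD and is not.

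A woman who never receives an IUD has no insertion to count from, so most of her serious events would not qualify either.

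At stake is whether a reader can take the table as a summary of the two randomised strategies. Events that belong to the postpartum period rather than to the device would appear more often under early placement. Pregnancy while waiting for the device, which sections 2.1 and 2.2 give as a reason for the trial, is not mentioned in 9.4.4.

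**Working it through.** The plan states no start date or exposure time for the safety table, so there is no planned figure to reproduce. The size follows from the insertion windows.

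**Inputs**
- Insertion windows (section 9.3): early days 14–28, midpoint (14 + 28)/2 = 21; interval days 42–56, midpoint (42 + 56)/2 = 49.
- Randomisation (section 8.1): by day 10; day 10 is used below.
- End of follow-up (section 4.3): 6 months postpartum, taken as day 180 (assumption). Day 240, the latest outcome contact in section 9.3, is used as an upper bound.
- Arm size 202 and 5% with no IUD placed (section 9.2).

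**Difference in start of counting, if treatment-emergent means after insertion**
- Window start: 42 − 14 = 28 days. Window end: 56 − 28 = 28 days. Midpoint: 49 − 21 = 28 days.
- For individual pairs of women it ranges from 42 − 28 = 14 to 56 − 14 = 42 days.
- If the term means from screening or randomisation, the difference is 0.

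**Post-insertion time at mid-window = end of follow-up − insertion midpoint**

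| End of follow-up | Early | Interval | Interval shorter by |
|---|---|---|---|
| Day 180 | 180 − 21 = 159 | 180 − 49 = 131 | 1 − 131/159 = 17.6% |
| Day 240 | 240 − 21 = 219 | 240 − 49 = 191 | 1 − 191/219 = 12.8% |

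**Time after randomisation that is collected but not counted (day 10 to insertion, of 180 − 10 = 170 days)**
- Early: 21 − 10 = 11 days at mid-window, 11/170 = about 6% (range 4 to 18 days).
- Interval: 49 − 10 = 39 days at mid-window, 39/170 = about 23% (range 32 to 46 days).

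Both arms lose time on this reading; the interval arm loses 28 days more.

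**Women with no IUD**
- 0.05 × 202 = 10.1, so about 10 per arm.

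**Number of events, for illustration**

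The documents give no expected SAE rate. Assume 1% of women per arm have an SAE, spread evenly over the 170 days. The 1% is the DSMB trigger level in section 8.2, not a forecast. Treat all 202 women per arm as having the device placed and being followed.
- Early: 202 × 0.01 × 159/170 = 1.89 events tabulated.
- Interval: 202 × 0.01 × 131/170 = 1.56 events tabulated.
- Difference: 202 × 0.01 × 28/170 = 0.33 events.
- At 2%: 3.78 against 3.11, a difference of about 0.67.
- At 1%, if the hazard in the 28 extra days were five times the average: 5 × 0.33 = about 1.7 events.

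**After the change**

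Counting from randomisation by assigned arm makes the start difference 0. Each arm then has about 170 to 180 days of observation, and the roughly 10 women per arm with no IUD are included.

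**The case against.** The best defence is that the late start is not in the text. The only AE baseline the protocol states is screening (section 8.3.4). If that baseline governs the table, counting starts at enrolment in both arms and the difference disappears. This stands as a possible reading. It does not settle the matter: the ordinary meaning of the term is onset after the intervention, and section 6.1 makes the intervention IUD placement. Leaving the choice open in a non-blinded trial also allows it to be made after events are known.

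The table also has a second category, AEs leading to discontinuation of the intervention. Section 7.1, under the heading on discontinuing the intervention, describes a woman who decides against placement. A pre-insertion event that stops placement may therefore be tabulated. This stands. A reader might infer that women with no IUD vanish from the table; the documents support only that most of their SAEs would be omitted.

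No test is planned on this table, and other provisions do not depend on the term. Perforation is analysed like the primary outcome (9.4.3), pelvic infection has its own hypothesis (9.1), the DSMB trigger uses any SAE (8.2), and SAEs go to the IRBs (8.3.6). This stands and limits the consequence to reporting.

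For device events such as perforation, counting from insertion gives both arms the same time origin. This stands too; there the arms differ mainly in length of follow-up.

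On pregnancy, the protocol does not class it as an AE, and the plan has no list of tables, so silence in 9.4.4 does not show that it will go unreported. The risk in section 2.3.1 of which the protocol says "This is true only during the standard of care" is that of placing an IUD in a woman who is already pregnant, which is narrower than pregnancy during the wait. Adding pregnancies is therefore a sensible completion of the table, not the correction of a stated exclusion.

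**Conclusion.** The concern holds for background postpartum events and for SAEs in women with no IUD, provided treatment-emergent carries its usual meaning. Counting then starts 28 days later in the interval arm, and post-insertion time is 17.6% shorter there to day 180 (12.8% to day 240). If background events occur at the same rate in both arms, the imbalance counts against early placement. In number of events it is probably small: well under one at a 1% or 2% SAE rate spread evenly, and below two at 1% with a fivefold early hazard. Those rates are assumptions.

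A reader might infer that the plan fixes a start about four weeks later for the interval arm and that the arms' safety data are not comparable at all. The documents support neither. The term is undefined, a zero-offset reading is available, and insertion-anchored counts are reasonable for device events. What the documents do show is an undefined filter which, as usually understood, depends on the randomised factor, and no specified safety summary from randomisation by assigned arm. It should be corrected because the correction is cheap, not because a large distortion has been shown.

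**What to change.** In section 9.4.4:

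1. Make the main safety table all SAEs from randomisation to the 6-month visit, by assigned arm, with all randomised women in the denominator whether or not an IUD was placed. Show pregnancies over the same period.
2. Keep the tabulation of AEs leading to discontinuation, and say whether it includes events before insertion that prevent placement.
3. Define treatment-emergent as onset after insertion and show those events in a separate table, with the number of women who received an IUD and the time at risk stated for each arm.

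The cost is a few lines in the plan and one extra table. No new data collection is needed: section 8.3.4 already requires AEs to be documented throughout the study, and section 8.1 already has pregnancy assessed at 6 months.

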9.4.5 BASELINE DESCRIPTIVE STATISTICS

Baseline characteristics such as demographic information (age, education level, race, ethnicity and employment status) will be collected. At the time of enrollment, questions will also be asked about pregnancy history, past use of contraception, breastfeeding status and future fertility desires. Means and proportions of respondents in each of the two groups will be compared to assess for success of randomization.

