9.2 SAMPLE SIZE DETERMINATION

We hypothesize that EPP IUD expulsion will be non-inferior to interval insertion. We propose that greater than or equal to a 6% difference in expulsion at 6 months postpartum between the two arms is clinically meaningful (6% non-inferiority margin). Therefore, we estimate that 404 women will be needed [202 in each arm] to achieve an 80% power to detect a difference of 6% in expulsion at 6 months at a significance level of .05 (two-sided alpha), assuming a 15% loss to follow up and that 5% of IUDs would not be placed after randomization (due to patient preference or new medical contraindication or inability to place the IUDs) and assuming a 4% expulsion rate in the interval group. We estimate that enrolling 404 patients allows us to achieve an 80% power to detect a difference of 6% or more between groups with a 1-sided type 1 error of 0.25%.

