9.4 STATISTICAL ANALYSES

9.4.1 GENERAL APPROACH

9.4.2 ANALYSIS OF THE PRIMARY EFFICACY ENDPOINT(S)

Our primary outcome, the proportion of women with complete IUD expulsion at 6 months after delivery in the two groups, will be compared in the modified intention-to-treat (MITT) cohort using the Wald test. Women who change their mind about receiving the IUD after randomization, choose to receive the IUD after 6 months, or women who choose not to participate in the study any time after randomization, will be excluded from analysis for the MITT analysis. In addition, we will present a per-protocol analysis. The per-protocol analysis will include women who received their treatment according to the timeframe in which they were randomized. For the early IUD insertion group, per-protocol analysis will include women with documented receipt of the IUD insertion between 14 and 28 days postpartum. For the interval IUD insertion group, the per-protocol analysis will include only women with documented receipt of a postpartum IUD between 42-56 days postpartum. In both the MITT and per-protocol analyses IUD expulsion rates will be compared using the 2-sided test of noninferiority. If the CI for the risk difference does not cross the prespecified 6% margin, noninferiority will be confirmed.

We will consider imputing missing data. However, if one group had no or few expulsion outcomes the model may not converge.

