9.4.3 ANALYSIS OF THE SECONDARY ENDPOINT(S)

Partial IUD expulsion and perforation will be analyzed with the same methods as the primary outcome. IUD discontinuation over the six-month study period will also be analyzed using survival analysis. Data will be censored either (1) at the last date of contact if a participant is lost to follow up or (2) time of IUD removal. The Log-rank test will be used for an unadjusted comparison of the two survival functions. This will be presented graphically using Kaplan-Meier curves.

For other secondary outcomes, normally distributed, continuous variables will be compared using Student's t-tests as appropriate. The Mann-Whitney U test will be used to compare other continuous variables that are not normally distributed. Proportions will be compared using chi-square tests. For small cell sizes, Fisher's exact test will be used as appropriate.

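### Baseline data serve only to check randomisation: no secondary comparison is adjusted, and nothing commits the plan to describing the analysis sets selected after randomisation

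*Combined protocol and SAP*

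**What the plan says.** Section 9.4.5 opens with an open-ended list: "Baseline characteristics such as demographic information (age, education level, race, ethnicity and employment status) will be collected". It adds that at enrolment "questions will also be asked about pregnancy history, past use of contraception, breastfeeding status and future fertility desires". It then states the one use of these data: "Means and proportions of respondents in each of the two groups will be compared to assess for success of randomization". It gives no test, significance level, threshold or action, and does not say which analysis set the two groups are.

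The outcome analyses make no use of these data. In 9.4.2 the primary outcome "will be compared in the modified intention-to-treat (MITT) cohort using the Wald test", with no covariates or strata named. In 9.4.3, for discontinuation, "The Log-rank test will be used for an unadjusted comparison of the two survival functions"; the other secondary outcomes get t, Mann-Whitney, chi-square or Fisher tests. Section 6.2 stratifies the randomisation by IUD type and site, but neither factor reappears in section 9.

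The MITT set is defined in 9.3 as "Participants who received an IUD within 6 months of delivery with known outcomes at the 6 month follow up visit", and 9.4.2 adds that "women who choose not to participate in the study any time after randomization, will be excluded from analysis for the MITT analysis". The per-protocol set also requires insertion within the assigned window. Even the set labelled intention-to-treat requires a known outcome.

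**The concern.** Three things are put to less use than they could be.

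- **The stated purpose.** When allocation is sound, baseline differences arise by chance, so their presence or absence says little about whether randomisation worked. With no threshold or action given, any judgement would be made after seeing the data.
- **The sets that carry the results.** The MITT and per-protocol sets depend on events after randomisation: receiving an IUD, when it was placed, and having a known outcome. Placement falls at 14-28 days in one arm and 42-56 days in the other, so interval women have about four more weeks in which to change their minds or drop out. Readers will want to see who is in each set and who left, by arm. The plan does not promise this.
- **The unadjusted comparisons.** Covariates that may predict IUD use, discontinuation, satisfaction, pain and bleeding are collected, and two stratification factors are known for every woman. Leaving them out gives up whatever precision they offer.

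At stake are the precision of the secondary results and the reader's ability to judge selection. No decision in the plan depends on the baseline comparison.

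**Working it through.** The plan states no figure on this point, so there is none to reproduce.

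**1. Women outside the MITT set.** Inputs from 9.2: 404 randomised, 15% lost to follow-up, 5% with no IUD placed.

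- If the losses act independently: 1 - 0.85 × 0.95 = 0.1925, and 0.1925 × 404 = 78 women.
- If they simply add: 0.15 + 0.05 = 0.20, and 0.20 × 404 = 81 women.

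About 19-20% are therefore expected to leave. The documents give no split by arm or by baseline characteristic, so this is the size of the selected-out group, not the size of any bias.

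**2. Why the primary comparison should stay unadjusted by these covariates.** Take the 4% interval-group rate from 9.2 and assume it in both arms. Expected expulsions are 0.04 × (404 - 81) = 12.9 to 0.04 × (404 - 78) = 13.0, about 13 in all. Four sites need three terms. IUD type (two levels), age, parity and previous IUD use (one term each) need four more. That is seven covariate terms plus arm against about 13 events, which is too sparse.

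**3. Possible precision gain for secondary outcomes.** For linear-type comparisons, covariates that explain a share R² of outcome variance multiply the residual variance by 1 - R². This is equivalent to enlarging the sample by 1/(1 - R²). The documents give no R²; 5-15% is an assumption.

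| R² (assumed) | 1/(1 - R²) | Equivalent gain in women |
|---|---|---|
| 0.05 | 1/0.95 = 1.053 | about 5% |
| 0.15 | 1/0.85 = 1.176 | about 18% |

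The formula does not carry over directly to Cox regression.

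**4. How often baseline testing would raise a false flag, if tests were done.** Section 9.4.5 names nine items (five demographic, four history). The 5% level is borrowed from 9.2, where it is set for the sample size ("at a significance level of .05 (two-sided alpha").

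- Nine independent tests: 1 - 0.95⁹ = 1 - 0.630 = 0.370.
- Nine tests with common correlation 0.3 (simulation, 400,000 draws): about 0.325.
- Nine tests with common correlation 0.5: about 0.268.

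The range for nine items is about 27-37%. This is an illustration only.

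**5. Which covariates are safe.** In 8.1 the baseline questionnaire follows the opening of the envelope. Women enrolled by phone may answer at any time before the first study visit, which is scheduled at 2 or 6 weeks depending on arm. Breastfeeding status and fertility desires could therefore reflect assignment or timing. Age, parity and previous IUD use cannot be changed by allocation.

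**The case against.** The strongest reply is that 9.4.5 is a short descriptive section and that much can be read into it that it does not say.

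- *A reader might infer that the check will declare randomisation failed in about 37% of sound trials.* The documents do not support this. No test, level or action is stated, the list of items is open, and related items are unlikely to be independent. If the comparison is purely descriptive, there is no such rate.
- *A reader might infer that baseline data will not be described, or will be described for the wrong groups.* The section is headed as descriptive statistics and reports means and proportions by group. It is silent on the analysis set, so the gap is a missing commitment, not a wrong choice.
- *A reader might convert the precision gain into a rise above 80% power.* That 80% belongs to expulsion, the outcome that should stay unadjusted here. The plan states no power for the secondary outcomes.
- *It can be said that a baseline comparison is not worthless.* This stands. Research assistants open the envelopes, and a gross imbalance could weakly signal tampering. The comparison is a poor tool for the question, not a useless one.
- *Unadjusted secondary comparisons are legitimate.* This also stands. Adjustment is a low-cost improvement, not the correction of an error.

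The reply leaves three facts in place: the single stated purpose, the absence of any commitment to describe the selected sets, and the absence of adjustment.

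**Conclusion.** The point holds as a minor one. The only stated purpose of the baseline data is one they serve poorly. The plan does not undertake to show baseline data for the MITT and per-protocol sets, although about 19-20% of women are expected to fall outside the MITT set. No comparison uses the collected covariates or the stratification factors.

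Only the adjustment can change a result. Its value is about 5-18% more women for linear-type comparisons, entirely conditional on the assumed 5-15% of variance explained; covariates that predict little would gain little. Dropping the randomisation wording and widening the table improve reporting but alter no estimate.

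Nothing here shows that the selected sets are in fact imbalanced, or that adjustment would remove a selection bias if there were one. The primary non-inferiority conclusion does not depend on this point.

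**What to change.** **In 9.4.3**, prespecify adjustment of the secondary comparisons with enough events (IUD use, discontinuation, satisfaction, pain and bleeding) for the stratification factors (IUD type as recorded for randomisation, and site) and for age, parity and previous IUD use.

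- Continuous outcomes: linear regression.
- Binary outcomes: logistic regression, reported as standardised risk differences.
- Discontinuation: a covariate-adjusted Cox model beside the log-rank test, with a note that it estimates a conditional hazard ratio.

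Do not adjust for breastfeeding status or fertility desires. Say that the primary comparison stays unadjusted by these covariates because few events are expected.

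**In 9.4.5**, replace the sentence on randomisation with a descriptive table by arm, without tests, for all randomised women, the MITT set, the per-protocol set and the women excluded from each.

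**Cost.** SAP wording, a few more model terms and a wider table. No change to sample size, margin or primary test. No new data should be needed, provided that parity and previous IUD use can be taken from the pregnancy-history and contraceptive-history questions. Section 9.4.5 does not name them separately, so check the questionnaire.
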